6.3.3.7 Inflammatory Bowel Disease Questionnaire (IBDQ) Score

IBDQ is used to assess IBD status. IBDQ is a valid and reliable quality of life instrument that incorporates social, systemic and emotional symptoms together with bowel-related symptoms into activity index. The IBDQ includes 32 questions on 4 areas of health-related quality of life:

Bowel Systems (10 questions: 1, 5, 9, 13, 17, 20, 22, 24, 26, 29),
Emotional Health Function (12 questions: 3, 7, 11, 15, 19, 21, 23, 25, 27, 30, 31, 32),
Social Function (5 questions: 4, 8, 12, 16, 28), and
System Function (5 questions: 2, 6, 10, 14, 18). Each item is rated on 7-point Likert scale (higher scores equate to higher quality of life).

A total IBDQ score is calculated as sum of all 32 scores and the total ranges from 32 to 224. If more than 4 questions are missing, then total scores will not be calculated. If 4 or fewer questions are missing, then missing questions will be imputed by the mean of the rest of available question scores.

Summary descriptive statistics including mean, standard deviation, median and range (including 95% confidence intervals) will be presented in tables and bar graphs for the actual observed and change from baseline scores for each domain and overall by treatment and by visit.

The change from baseline IBDQ score will be analyzed using an analysis of covariance (ANCOVA) model with treatment group, stratification variable anti-TNF agents use (yes/no) as classification factors, and baseline IBDQ score as a covariate. The treatment parameter estimates from the analysis model including means, 95% confidence intervals and associated 2-sided p-values will be presented.

6.3.3.8 Serum Marker of Inflammation: C-reactive Protein (CRP)

The CRP is used as marker of inflammation. The C-reactive Protein (CRP) level data collected at different visits will be used to assess inflammation at baseline and at different visits post-baseline. Summary descriptive statistics for the actual observed and change from baseline will include mean, standard deviation, median and range for each treatment by visit. The change from baseline CRP comparing the two treatment groups will be analyzed using an analysis of covariance (ANCOVA) model with treatment group, stratification variable anti-TNF agents use (yes/no) as classification factors, and baseline CRP as a covariate. The treatment parameter estimates from the analysis model including means, 95% confidence intervals and associated 2-sided p-values will be presented including bar graphs.

In addition, the CRP level will be classified into two categories: “Normal (≤ 0.999 mg/dL)” and “High (> 10 mg/dL)”. Summary results will show number of patients and proportion (%) with “Normal level” and with “High Level” by treatment group at baseline and at different visit time-points with data collected post-baseline. The same statistical method and modeling as used for the primary endpoint will be used for this analysis. The proportion of subjects “Normal” at baseline and at each visit with data post-baseline will be compared between the two treatments using Cochran-Mantel-Haenszel (CMH) chi-square test controlling for the stratification variable anti-TNF agents use (yes/no).

Supplementary shift tables will be presented showing proportion of subjects at baseline that were in each category and shifted from one category to another or remained in the same category at the different post-baseline visits.

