Study Population:	Subjects with active, moderate to severe Crohn's Disease (CD). The following inclusion criteria apply: • Males and females 18 to 75 years of age. • Signed fully informed consent provided as per this protocol. • Diagnosis of Crohn's Disease confirmed by endoscopy or radiography and/or histology at least 6 months prior to randomization into the study. • CD involving the ileum and/or colon • Moderately to severely active CD (Crohn's Disease Activity Index (CDAI) score of ≥ 220 and ≤450) at baseline. • Current treatment with at least one of the following therapies: • Oral 5-aminosalicylic acid (5-ASA) compounds • Dose must be stable for at least 4 weeks before baseline • Corticosteroid therapy • Dose must be stable for at least 2 weeks before baseline • Azathioprine or 6-mercaptopurine (6-MP) or methotrexate • Dose must be stable for at least 8 weeks before baseline • Infliximab or adalimumab • Dose must be stable for at least 14 weeks before baseline • White blood cell count ≥ 3.5x10° at screening. • Active Crohn's disease, defined by at least one of the following: C-reactive protein > Upper Limit of Normal (ULN) at screening, OR radiographic (MRE or CTE) or endoscopic confirmation of the presence of active CD within 5 weeks of screening visit. • Subject agrees to use the following effective contraceptive methods only • diaphragm, cervical cap, contraceptive sponge or condom with spermicidal foam/gel/cream/suppository • IUD/IUS • progestogen injection (Depo-Provera®) throughout the study and for at least 6 weeks after last study drug administration, unless subject or partner of subject is post-menopausal or otherwise incapable of becoming pregnant by reason of surgery or tubal ligation, or has had a vasectomy. In regions where local regulatory						
	contraceptive requirements differ, the ICF will reflect local policies. The following key exclusion criteria apply: Crohn's disease involvement isolated to the mouth, upper gastrointestinal tract, or anus.						

	History of total colectomy with ileorectal anastomosis or a proctocolectomy.				
	 Presence of active fistulizing Crohn's Disease or healed fistula within 2 m prior to screening. 				
	Subject has postoperative stoma, ostomy, or ileoanal pouch.				
	Subject has short bowel syndrome.				
	Subject is scheduled for surgical bowel resection.				
	 Subject has known symptomatic obstructive strictures or bowel perforation in the 6 months prior to screening. 				

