2.1.3 Other Supportive Secondary Efficacy Objectives

1. To compare the arm-specific time to remission and time to response.
2. To compare the arm-specific duration of remission and duration of response.
3. To compare the proportion of subjects who have maintained remission from week 16 through week 52.
4. To assess whether subjects randomized to receive RHB-104 have a higher probability of being in a state of response at the 16 week assessment as compared to subjects randomized to receive placebo.
5. To assess the difference between the treatment groups in health-related quality-of-life using the IBDQ and SF-36 questionnaire instruments.
6. To compare arm-specific endoscopic 26-week changes using the CDEIS and SES-CD score in those subjects who consent to undergo colonoscopy.
7. To assess the effect of RHB-104 on markers of inflammation.
8. To assess the proportion of subjects in steroid free remission in each treatment arm at week 26. Subjects must be maintained off steroids for 3 weeks in order to be determined to be in steroid free remission e.g. by week 23.

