6. STATISTICAL METHODOLOGY

6.1 Statistical and Analytical Issues

6.1.1 Statistical Methods

Descriptive statistics summary results will be produced and presented for all the data collected on the different assessments that include demographics, baseline characteristics, concomitant medications, efficacy, and safety endpoints. Continuous data summary descriptive statistics will

include the number of observations, means, standard deviations, medians, and ranges. Categorical variables will be summarized with frequencies and percentages.

The primary hypothesis testing will be two-sided statistical significance testing (alpha level = 0.05) comparing active treatment to placebo and mainly dedicated to assessing the primary endpoint and the key secondary endpoints. Point and interval estimates (95% confidence intervals) will be calculated and presented by treatment group for each parameter. Computed p-values will be rounded to four decimal places; p-values less than 0.0001 will be presented as '< 0.0001' and p-values greater than 0.9999 will be presented as '> 0.9999' in the tables.

All statistical analyses will be performed using SAS statistical software (Version 9.3 or an updated latest higher version available at the time of analysis). Adverse events will be coded using the most recent MedDRA version available at the time of analysis and the version used will be footnoted in the respective summary tables. Concomitant medications will be coded using the most recent version of World Health Organization (WHO) Drug dictionary.

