6.3.3.9 Stool Marker of Inflammation: Fecal calprotectin

The fecal calprotectin is used as marker of inflammation. The level of fecal calprotectin data collected at different visits will be used to assess inflammation at baseline and at different visits post-baseline. Summary descriptive statistics for the actual observed and change from baseline will include mean, standard deviation, median and range for each treatment by visit. The change from baseline Fecal calprotectin comparing the two treatment groups will be analyzed using an analysis of covariance (ANCOVA) model with treatment group, stratification variable anti-TNF agents use (yes/no) as classification factors, and baseline Fecal calprotectin as a covariate. The treatment parameter estimates from the analysis model including means, 95% confidence intervals and associated 2-sided p-values will be presented including bar graphs.

In addition, fecal calprotectin will be classified into two categories: “Normal (≤ 162.9 mcg/g)” and “High (> 162.9 mcg/g)”. Summary results will show number of patients and proportion (%) with “Normal level” and with “High Level” by treatment group at baseline and at different visit time-points with data collected post-baseline. The same statistical method and modeling as used for the primary endpoint will be used for this analysis. The proportion of subjects “Normal” at baseline and each visit with data post-baseline will be compared between the two treatments using Cochran-Mantel-Haenszel (CMH) chi-square test controlling for the stratification variable anti-TNF agents use (yes/no).

Supplementary shift tables will be presented showing proportion of subjects at baseline that were in each category and shifted from one category to another or remained in the same category at the different post-baseline visits.

6.3.3.10 Endoscopic Assessment Based on CDEIS and SES-CD at Week 26

The Crohn's Disease Endoscopic Index of Severity (CDEIS) is a validated quantitative measure of disease severity upon endoscopy. The score ranges from 0-44 based upon the extent and severity of inflammation and ulcers seen during endoscopy of the colon. A response is a drop in score from baseline.

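### CRP and fecal calprotectin are analysed on the raw scale only; if the markers are strongly right-skewed and the effect is proportional, a pre-specified log-scale ANCOVA would be more efficient

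*SAP*

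**What the plan says.** The SAP lists among its supportive secondary objectives (2.1.3): "To assess the effect of RHB-104 on markers of inflammation". Two markers carry it.

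- **CRP (SAP 6.3.3.8):** "The change from baseline CRP comparing the two treatment groups will be analyzed using an analysis of covariance (ANCOVA) model with treatment group", with the anti-TNF stratum as a second factor "and baseline CRP as a covariate".
- **Fecal calprotectin (SAP 6.3.3.9):** "The change from baseline Fecal calprotectin comparing the two treatment groups will be analyzed using an analysis of covariance (ANCOVA) model", again with the stratum "and baseline Fecal calprotectin as a covariate".

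Neither section states a log or other transformation, a ratio of geometric means, a rank method, a distributional check, or a rule for results below the assay limit. As written, the outcome and the covariate are both on the raw scale.

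Both sections also plan descriptive summaries. The CRP text reads: "Summary descriptive statistics for the actual observed and change from baseline will include mean, standard deviation, median and range for each treatment by visit". Both add a stratified CMH comparison of the proportion in the normal category, and shift tables. SAP 6.3.3 treats this whole group of endpoints as descriptive or supportive, without multiplicity adjustment.

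**The concern.** The same model is used for the SF-36 and IBDQ scores (SAP 6.3.3.6 and 6.3.3.7). Those scores have a floor and a ceiling. CRP and calprotectin are concentrations, with a floor at zero and no fixed upper end. The Protocol's entry criterion for active disease, "C-reactive protein > Upper Limit of Normal (ULN) at screening, OR radiographic (MRE or CTE) or endoscopic confirmation", lets both normal and raised CRP into the trial.

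If such a marker is strongly right-skewed, a few very high results supply most of the residual variance in a raw-scale ANCOVA. If treatment lowers values by a roughly constant percentage, the effect is also not a constant difference on the raw scale. A real reduction in inflammation could then go undetected, or be estimated with a very wide interval. These are laboratory measures scheduled for all subjects, whereas the endoscopic scores come only from those who consent to colonoscopy.

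**Working it through.** **The plan's own figures.** The documents give no power, SD, range or expected effect for either marker. Their only sample-size figure concerns week 26 remission, 21% versus 36%:

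- n = [1.960·√(2·0.285·0.715) + 1.282·√(0.21·0.79 + 0.36·0.64)]² / 0.15² ≈ 189 per arm. With continuity correction it is 202 per arm (404 in total), or 203 (406) at alpha 0.049. The plan's 205 (410) is within 3% of this.
- At 162 per arm the power is 85%, consistent with the stated figure of at least 80%.

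This confirms 162 per arm as a sound input. It says nothing about CRP or calprotectin.

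**Inputs for the markers**

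- From the documents: 162 per arm and 1:1 allocation. The test is two-sided at 0.05 (SAP 6.1.1: "The primary hypothesis testing will be two-sided statistical significance testing (alpha level = 0.05) comparing active treatment to placebo").
- Assumed: log-normal marker, the log-SD (s), the baseline-to-follow-up correlation (ρ) on the log scale, the treatment effect, 20% anti-TNF use, and every subject measured.

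**Method.** 2,000 to 3,000 simulated trials per setting. Raw ANCOVA (change on treatment, stratum and baseline) and log ANCOVA (the same with logged values) were fitted to the same data.

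**Setting A: 30% lower geometric mean, ρ = 0.6**

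The log-scale power can be checked by hand: power ≈ Φ(−ln 0.7 / [s·√(1−0.6²)·√(2/162)] − 1.96) = Φ(0.3567 / (0.0889·s) − 1.96). At s = 1.0 this is Φ(2.05) = 98%; at 1.25, Φ(1.25) = 89%; at 1.5, Φ(0.72) = 76%. The simulations agree. Ranges show variation between runs.

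| log-SD | Raw power | Log power | Share of raw residual sum of squares from 16 of 324 subjects (5%) |
|---|---|---|---|
| 0.3–0.6 | about 100% | about 100% | – |
| 0.8 | about 98% | about 100% | – |
| 1.0 | 81% | 98% | 69% |
| 1.25 | 51–54% | 88–90% | 78% |
| 1.5 | about 30% | about 75% | 84% |

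**Setting B: effect sized for 80% log-scale power, ρ = 0.5**

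This avoids the ceiling near 100% at low log-SD. The geometric mean ratio is exp(−(1.960 + 0.842)·s·√(1−0.5²)·√(2/162)); at s = 0.5 it is exp(−0.135) = 0.874.

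| log-SD | Geometric mean ratio | Raw power | Log power | Approximate multiple of N for raw to reach 80% |
|---|---|---|---|---|
| 0.3 | 0.922 | 77% | 79% | – |
| 0.5 | 0.874 | 72% | 80% | 1.2 |
| 0.8 | 0.806 | 62% | 80% | 1.5 |
| 1.0 | 0.764 | 55% | 78% | 1.8 |
| 1.2 | 0.724 | 46% | 78% | 2.3 |
| 1.5 | 0.667 | 34% | 80% | 3.3 |

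The SD of the estimated effect divided by its mean, raw versus log, was 0.40 versus 0.35 at log-SD 0.5, 0.51 versus 0.37 at 1.0, and 0.80 versus 0.36 at 1.5.

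**Setting C: no effect.** Raw-scale type I error was 4.0–5.4% for log-SD 0.5 to 1.5.

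**Setting D: other effect shapes**

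- Only the upper third of follow-up values falls, with the excess over the cut reduced by 80%, at log-SD 1.0: raw 95%, log 42%.
- A roughly normal marker with an additive shift: raw 79–81%, log 65–78%.

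**The case against.** The strongest reply is that this is a modelling preference resting on unproven assumptions. Much of it is fair.

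- **The spread and effect shape are assumed.** A reader might infer that the log scale always gives far more power and a steadier estimate. The documents do not support that. They give no SD, and settings A and B build in the model that favours the log scale. Setting D reverses the order. This stands, and it makes the point conditional.
- **The CRP categories are not evidence of spread.** A reader might take the labels in SAP 6.3.3.8 (normal at 0.999 mg/dL or less, high above 10 mg/dL) as showing a tenfold range. They are two cut-offs with unclassified values between them and say nothing about the distribution.
- **Type I error.** A reader might infer that outliers produce false positives beyond the nominal rate. Setting C shows otherwise: the planned test is valid.
- **The plan already has outlier-resistant summaries.** It has medians, the CMH comparison and shift tables. For calprotectin, with its single cut at 162.9 mcg/g, the comparison is fully defined. For CRP the gap between cut-offs must first be closed. In either case dichotomising does not replace a continuous analysis.
- **The quantity estimated changes.** The log analysis gives a ratio of geometric means, not a mean difference, and it may depend on how values below the assay limit are handled. Both points stand. Keeping the raw ANCOVA as supplementary answers the first, and a stated rule addresses the second.

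**Conclusion.** The point holds in conditional form. The plan fixes a raw-scale ANCOVA for both markers and offers no skew-robust continuous analysis. The test is valid but can be inefficient. If log-SD is about 0.8 or more and the effect is roughly proportional, the loss in setting A runs from about 2 power points at log-SD 0.8 to 17 at 1.0 and about 45 at 1.5. With a smaller effect (setting B) it is already 18 points at log-SD 0.8. At log-SD 0.5 or below it is small, and it reverses if treatment acts mainly on the highest values.

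All of this rests on an assumed log-normal marker, the stated correlations and complete data at 162 per arm. The markers are supportive and unadjusted for multiplicity, so no primary or key secondary conclusion changes. This is a cheap improvement, not a correction of an invalid analysis.

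**What to change.** In SAP 6.3.3.8 and 6.3.3.9, before unblinding:

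1. Pre-specify, at each post-baseline visit with data, an ANCOVA of log(marker) with log(baseline), treatment and anti-TNF stratum.
2. Report the ratio of geometric means with its 95% CI. With log baseline in the model, the treatment estimate is the same whether the outcome is the log value or the change in log value, so the comparison remains one of change from baseline.
3. State how values below the assay limit are set, for each marker.
4. Keep the planned raw-scale ANCOVA as supplementary and the raw summaries as descriptive.

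Separately, reconcile the CRP category cut-offs, since values above 0.999 and up to 10 mg/dL currently fall in neither category.

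The cost is SAP wording and additional output. No extra data are needed, and SAP 6.8 provides for changes made before unblinding. The downside is that the effect is read as a ratio and may be sensitive to the below-limit rule.

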4.1.1 Study Visit Schedule

	Screening (Day -42 to screening Day -7)	Baseline Day 1 / Week 0 ⁶	Week 2	Week 4	Week 6	Weeks 8, 12, 16 and 20	Week 26	Weeks 35 and 44	Week 52	Week 56
Study Visit Window			± 3 days	± 3 days	± 3 days	± 7 days	± 7 days	± 7 days	± 7 days	± 7 days
Informed Consent	X									
Inclusion/ Exclusion Criteria Demography and Medical History	X	X								
Concomitant Medications Assessment	X	X	X	X	X	X	X	X	X	X
Vital Signs and Physical Examination	X	X	X	X	X	X	X	X	X	X
Adverse Event Assessments			X	X	X	X	X	X	X	X
CDAI collection ¹		X		X		X	X	X	X	
Subject Assessments: IBDQ and SF-36		X					X		X	
Uveitis Assessment	X	X	X	X	X	X	X	X	X	X
ECG ²	X	X	X	X		Weeks 8 and 12	X		X	
Hematology and Biochemistry	X	X	X	X	X	X	X	X	X	X
Urinalysis ³	X	X	X	X	X	X	X	X	X	X
Plasma Levels of RHB-104 ⁴							X			
Hep B S Ag, Hep C Ab, HIV and QuantiFERON®-TB	X									
C-Reactive Protein (CRP)	X	X				X	X	X	X	
MAP Testing Blood with Additional Sample for Future Use		X		X		X	X	X	X	
MAP culture from blood		X					X		X	
Fecal calprotectin	X	X				Week 12	X		X	
Stool Testing other ⁵	X						X		X	
Pregnancy Test Urine	X	X	X	X	X	X	X	X	X	X
Colonoscopy ⁶ and CDEIS, storage of images, MAP testing , archive samples and possible analysis of drug levels		X					X			
Population PK Blood Sampling ⁴			X	X	X	Week 8, 12 and 20		X	X	X ⁸
Randomization (after meeting inclusion/exclusion criteria) ⁷		X								

Study Drug and Diary Dispensing (with instructions for drug administration & diary completion ¹)	Diary only	X	X	X	X	X	X	X		
Drug Return & Accountability			X	X	X	X	X	X	X	
Telephone reminder of dose escalation		Day 7	Day 21							

¹ **CDAI:** Subjects will complete a CDAI diary for the 7 days preceding their next study visit. To ensure compliance, site personnel will contact subjects prior to initiation of the CDAI-recording period, to review the process for adequate CDAI data collection. At the screening visit the 7-Day CDAI diary will be distributed to the subject for completion before the Baseline visit and if applicable, before the colonoscopy preparation/procedure takes place.

² **ECG:** Five minute continuous digital 12-lead ECG after resting 10 minutes in a supine position

³ **Urine Testing:** Dipstick test only, unless results are abnormal

⁴ **Frozen plasma sample:** For Week 26 clarithromycin, rifabutin, clofazimine, 14-hydroxy-clarithromycin, and 25-O-desacetyl-rifabutin plasma concentration measurement.

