6.5.2 Laboratory Parameters

Laboratory assessments will include:

Biochemistry: total protein, gamma glutamyl transferase (GGT), lactate dehydrogenase (LDH), sodium, potassium, chloride, magnesium, glucose, total bilirubin, AST(SGOT), ALT(SGPT), alkaline phosphatase, amylase, albumin, BUN, calcium, creatinine, uric acid, HCO₃, total cholesterol, creatinine phosphokinase, and inorganic phosphorous.

Hematology: RBC count, hemoglobin, hematocrit, platelet count, WBC count, WBC differential.

Urinalysis: Pregnancy, pH (dipstick), specific gravity (dipstick), glucose (dipstick), protein (dipstick), ketones (dipstick), blood (dipstick), Nitrites, Leucocytes and sediment microscopy if indicated by the dipstick.

Laboratory results will be presented in listings in measured units and summaries in conventional units.

Continuous laboratory values will be summarized descriptively by treatment group over time for each visit and as change from baseline to each visit. Categorical laboratory values will be summarized as the number and percentages of subjects in each category by treatment group over time for visit.

Laboratory parameters will also be summarized in shift tables by treatment, to determine the number and percentage of subjects with measurements classified in a particular category at each post-baseline visit with reference to the same classification at baseline. Biochemistry and hematology parameters (which are continuous in nature) will use the classifications of low, normal, and high relative to normal ranges, whereas appropriate categories will be selected for urinalysis parameters (which are categorical in nature), for example, normal and abnormal.

Subjects missing a value at any time point will be excluded from the summary statistics for that time point. If a subject has more than one value at any time point, then the latest non missing value will be used for summarization. All values will be presented in the data listings.

Listings of all individual laboratory data, indicating any values out of the normal range will be produced. A listing of lab parameter values flagged as abnormal will also be provided.

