Table 14.2.3.4.2	Summary Stool Marker of Inflammation Level - Fecal calprotectin: Intent-to-Treat Population
Table 14.2.3.4.3	Proportion of subjects with CRP Marker of Inflammation Normal/High by Visit by Treatment : Intent-to-Treat Population
Table 14.2.3.4.4	Proportion of subjects with Fecal calprotectin Normal/High by Visit by Treatment : Intent-to-Treat Population
Table 14.2.3.4.5	Shift in Serum Marker of Inflammation (CRP) Status Normal/High Baseline to

	Week 26 and Week 52: Intent-to-Treat Population
Table 14.2.3.4.6	Shift in Stool Marker of Inflammation (Fecal calprotectin) Status Normal/High Baseline to Week 26 and Week 52 : Intent-to-Treat Population
Figure 14.2.3.4.1	Scatter Plot: CRP vs. CDAI Total score baseline, weeks 26 & 52: Intent-to-Treat Population
Figure 14.2.3.4.2	Scatter Plot: Fecal calprotectin vs. CDAI Total score baseline, weeks 26 & 52: Intent-to-Treat Population
Supportive/Supplementary Endpoints: Quality of Life Assessment	
Table 14.2.3.5.1	Short Form (SF-36) questionnaire total score and domain scores at Baseline, Week 26 and Week 52: Intent-to-Treat Population
Table 14.2.3.5.2	Inflammatory Bowel Disease Questionnaire (IBDQ) Score at Baseline, Week 26 and Week 52: Intent-to-Treat Population
Figure 14.2.3.5.1	Bar Graphs of SF-36 Total Score and Domain Scores at Baseline, 26 and 52 Weeks by treatment group: Intent-to-Treat Population
Figure 14.2.3.5.2	Bar Graphs of IBDQ Score at Baseline, 26 and 52 weeks by Treatment group: Intent-to-Treat Population
Exploratory Endpoints: MAP Detection	
Table 14.2.4.1.1	Baseline and Change in MAP Blood PCR Assay Status After Weeks 26 and 52: Intent-to-Treat Population
Table 14.2.4.1.2	Baseline and Change in Blood Culture Status After Weeks 26 and 52: Intent-to-Treat Population
Table 14.2.4.1.3	Baseline and Change in MAP Colon Biopsy PCR Assay Status After Weeks 26 and 52: Intent-to-Treat Population
Table 14.2.4.2.1	Shift in MAP Blood PCR Assay Status From Baseline to Weeks 26 and 52: Intent-to-Treat Population
Table 14.2.4.2.2	Shift in Blood Culture Status From Baseline to Weeks 26 and 52: Intent-to-Treat Population
Table 14.2.4.2.3	Shift in Colon Biopsy PCR Assay Status From Baseline to Weeks 26 and 52: Intent-to-Treat Population
Table 14.2.4.3.1	Baseline Correlations Blood PCR Assay, Blood Culture Test, Colon Biopsy PCR Assay and CDAI: Intent-to-Treat Population

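### The two CRP categories do not meet: a value above 0.999 and up to 10 mg/dL is neither Normal nor High

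*SAP*

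**What the plan says.** SAP section 6.3.3.8 sets the rule: "the CRP level will be classified into two categories: “Normal (≤ 0.999 mg/dL)” and “High (> 10 mg/dL". It defines no third category and says nothing about values between the two limits. Three outputs rest on the rule:

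- Numbers and percentages of subjects who are Normal and High, by arm, at baseline and at later visits. SAP section 8.1 lists this as Table 14.2.3.4.3, "Proportion of subjects with CRP Marker of Inflammation Normal/High by Visit by Treatment".
- A test of the proportion Normal, which "at baseline and at each visit with data post-baseline will be compared between the two treatments using Cochran-Mantel-Haenszel (CMH) chi-square test", stratified by anti-TNF use.
- Shift tables: "Supplementary shift tables will be presented showing proportion of subjects at baseline that were in each category" and how they moved afterwards. Section 8.1 lists Table 14.2.3.4.5, "Shift in Serum Marker of Inflammation (CRP) Status Normal/High Baseline to" Weeks 26 and 52.

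Section 6.3.1 also names baseline CRP, as Normal/High, among the factors for the exploratory logistic models of Week 26 remission. It gives no limits there.

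The protocol's inclusion criteria use one CRP limit, "C-reactive protein > Upper Limit of Normal (ULN) at screening", without a numerical value or unit.

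**The concern.** A two-category rule should give every measured value exactly one category. This one does not. Nor does it look like a deliberate middle band, which would need a name, a count and its own row and column in the shift tables.

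The sister rules in the same part of the SAP show what was presumably meant. Section 6.3.3.9 splits fecal calprotectin at a single value, 162.9 mcg/g. Section 6.3.3.10 splits CDEIS at 3 and SES-CD at 2. Section 6.5.2 does not list CRP, but its approach points the same way: biochemistry and hematology parameters "will use the classifications of low, normal, and high relative to normal ranges".

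What is at stake is the supportive evidence on inflammation. Subjects in the band would drop out of both counts. A fall from High into the band, or from the band to Normal, could not be shown as a shift. If the choice of cut is left until results are visible, it also becomes a post hoc choice.

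**Working it through.** **Inputs.** Normal is CRP ≤ 0.999 mg/dL and High is CRP > 10 mg/dL (SAP 6.3.3.8). CRP is scheduled at baseline and at Weeks 8, 12, 16, 20, 26, 35, 44 and 52, which is 8 visits after baseline (SAP 4.1.1). There are two arms.

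**1. The rule as written.**

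| CRP (mg/dL) | Category |
|---|---|
| 0.999 | Normal |
| 1.0 | none |
| 5 | none |
| 10 | none |
| 10.001 | High |

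Gap width: 10 − 0.999 = 9.001 mg/dL. Ratio of limits: 10/0.999 = 10.01. On a grid from 0 to 30 mg/dL in steps of 0.001, 9,001 values (1.000 to 10.000) have no category and none has two. As a comparison, calprotectin of 162.9 mcg/g is Normal and 162.91 is High, so that rule has no gap.

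**2. The rule if the 10 was meant in mg/L.** 10 mg/L = 1.0 mg/dL, so the gap is 1.0 − 0.999 = 0.001 mg/dL. A result of 1.000 mg/dL is still unclassified. Depending on the reading, the gap is between 0.001 and 9.001 mg/dL wide.

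**3. The counts table.** (1 baseline + 8 later visits) × 2 arms = up to 18 arm-by-visit rows. In each, the shortfall is 100% − Normal % − High %, which is the share of measured subjects in the gap.

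**4. The shift table.** As written, a subject can be in three states: Normal, gap or High. That gives 3 × 3 = 9 possible transitions per visit, against 2 × 2 = 4 cells for Normal/High. Five transitions have no cell. Over Weeks 26 and 52, the visits in the table title, that is 10 of 18. Over all 8 later visits, as the text of 6.3.3.8 would allow, it is 40 of 72. These are possible transitions, not numbers of subjects.

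**5. The CMH test.** Write N, G and H for the numbers Normal, in the gap and High in one arm at one visit. With all measured subjects in the denominator, the proportion Normal is N/(N + G + H). The test can then be run, with gap values counted as not Normal, and it stays the same after correction provided the confirmed cut is 0.999 mg/dL. If only classified subjects are used, the proportion is N/(N + H), which is larger whenever N and G are both above zero, and the test can change. The SAP does not say which denominator applies.

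**6. Link to eligibility.** If 0.999 mg/dL is the laboratory's ULN, which is an assumption, a subject whose CRP counts as raised under the protocol could be at up to about 10 times ULN and still not be High in the SAP.

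**The case against.** The strongest reply is that this is a small slip in a supportive analysis and would surface as soon as the first table is programmed. Much of that stands. Section 6.3.3 calls these endpoints descriptive, with no multiplicity adjustment. Continuous CRP is still summarised by visit and analysed by ANCOVA. On the likely mg/L reading, or if a decimal point was lost from 1.0, almost no gap remains, so the limit is worth checking against the signed SAP. Neither explanation is confirmed in the documents, and both still leave a gap of 0.001 mg/dL, so the sentence needs correcting either way.

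Two further replies carry less weight. Section 6.3.1 leaves the categories of continuous variables to the time of analysis. That makes the effect on the logistic factor conditional, but it does not alter the fixed limits in 6.3.3.8, which are the only CRP Normal/High limits in the documents. Section 8 keeps the table layouts in a separate document, which may already deal with the problem. The point here is the SAP rule as written.

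**Conclusion.** The concern holds. As printed, the rule leaves values above 0.999 and up to 10 mg/dL without a category, so the counts table and shift tables are incomplete. The number of subjects affected is unknown and is not estimated here. The CMH comparison can be run if all measured subjects form the denominator, which the SAP should state. The logistic factor in 6.3.1 is affected only if it takes its limits from 6.3.3.8. Nothing in the primary or key secondary inference changes. This should be corrected, but it does not threaten the trial's main conclusion.

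**What to change.** In section 6.3.3.8, replace the two limits with one cut c in one unit: Normal if CRP ≤ c, High if CRP > c, in the same form as calprotectin. The sponsor should confirm c and its unit from the laboratory reference range. State that percentages and the CMH test use all subjects with a CRP value at the visit. Use the same derived variable for the Normal/High factor in section 6.3.1 and for Tables 14.2.3.4.3 and 14.2.3.4.5.

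The cost is one or two sentences of SAP text and no new data. Section 6.8 provides for changes made before unblinding, and the cut should be fixed by then.
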